5.11.2. CGM Variables and Analysis

The continuous variables derived from CGM will be summarized and compared between treatment groups by visit using MMRM model. The model will include the treatment, HbA1c stratum (<8.5% or >=8.5%), baseline value of the dependent variable, visit, and treatment by

visit interaction. The raw mean and LS mean difference between treatment groups will be summarized.

For the between-day and within-day glucose variability, the variable will take log-transformation before performing the MMRM analysis.

The binary variables will be analyzed using a longitudinal logistic regression. In the longitudinal logistic regression model, the independent variables of treatment, baseline HbA1c value, baseline continuous variable corresponding to the binary dependent variable, visit, and treatment by visit interaction will be used.

For the hypoglycemia episodes defined by CGM, the analysis using a negative binomial model with the offset of log (exposure in year) will be performed. The model will include treatment, baseline HbA1c, baseline incidence for the dependent variable.

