6.3. Measures to Minimize Bias: Randomization and Blinding

This is an open-label study; thus, it will be unblinded. However, the specific intervention to be taken by a participant will be assigned using an Interactive Web Response System (IWRS). The site will contact the IWRS prior to the start of study intervention administration for each participant. The site will record the intervention assignment in the appropriate data capture tool. Potential bias will be reduced by the following steps: central randomization, stratification, blinded adjudication for CV endpoints.

Patients who meet all criteria for enrollment will be randomized to treatment at Visit 3. Assignment to treatment groups will be determined by a computer-generated random sequence using the IWRS. The IWRS will be used to assign IP to each patient. Site personnel will confirm that they have located the correct IP by entering a confirmation number found on the IP label into the IWRS.

To achieve between-group comparability for site factor, the randomization will be stratified by baseline HbA1c (<8.5%, \geq 8.5%), and country. The randomization scheme will be performed using IWRS, which will ensure balance between treatment groups.

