5.7. Primary Outcome and Methodology

The primary objective is to compare the HbA1c change from baseline to Week 26 between LY3209590 and insulin degludec and will be based on the primary estimand described below.

The primary estimand is the treatment differences in the change in HbA1c from baseline to 26 weeks for the targeted study population if all patients would adhere to the treatment without intercurrent events. The analysis data will include data up to the discontinuation of study treatment for the Efficacy Population with baseline and at least one non-missing postbaseline measurement. There may be missing values due to the early discontinuation of study treatment. The MMRM model will be used with the HbA1c changes at Week 6, 12, 16 and 26 (the primary endpoint) and the missing values will be imputed implicitly in the MMRM analysis under the assumption of missing at random. The MMRM model will include treatment (LY3209590 Algorithm 1, insulin degludec), country, visit, and treatment by visit interaction and the baseline value of the dependent variable as the fixed effects. The HbA1c is reported in unit of % and will be converted to the unit of mmol/mol using the following formula: HbA1c in mmol/mol = 10.93*HbA1c in % - 23.5 (<http://www.ngsp.org/ifccngsp.asp>). HbA1c analysis will be conducted based on both units.

In the MMRM model, the within-patient errors are modeled as an unstructured variance-covariance matrix. If the analysis fails to converge, the following variance-covariance matrix will be used (in order) until one converges:

1. Toeplitz with heterogeneity
2. autoregressive with heterogeneity
3. compound symmetry with heterogeneous variances
4. Toeplitz
5. autoregressive
6. compound symmetry without heterogeneous variances

The Kenward-Roger approximation will be used to estimate denominator degrees of freedom for the MMRM models. The following is an example SAS code:

```
proc mixed data=DATA;
  class TREATMENT STRATIFICATIONS VISIT PATIENT;
  model HbA1c=BASELINE TREATMENT STRATIFICATIONS VISIT
    VISIT*TREATMENT / solution ddfm=kr;
  repeated VISIT / subject=PATIENT type=un;
  lsmeans TREATMENT*VISIT/ pdiff cl alpha=0.1 om=DATA;
run;
```

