5.8. Secondary and Additional Efficacy Analyses

The primary population for the secondary analysis on HbA1c reduction is the EAS. Treatment comparison at 26 weeks will be used to assess the differences. The 2-sided 90% CI for the LS mean of the differences in the change in HbA1c at 26 weeks will also be constructed.

The following secondary efficacy outcomes will be analyzed based on the EAS using the same MMRM model as the primary analysis with the addition term of HbA1c strata ($<8.5\%$ and $\geq 8.5\%$) for non-HbA1c measures:

1. HbA1c change from baseline to Week 12.
2. Fasting blood glucose (FBG) and change by SMBG from baseline to Week 12 and Week 26;
3. Fasting serum glucose (FSG) by laboratory and change from baseline at Weeks 12 and 26;
4. Between-day glucose variability measured by the SD and the CV of the FBG at Week 12 and 26;
5. Six-point SMBG profile (pre-meal and 2-hour postprandial SMBG measurements for the morning, midday, and evening meals) at Weeks 12 and 26.
6. Within-day and between-day glucose variability measured by the SD and the CV of 6-point SMBG.
7. Prandial insulin dose and change from baseline to Week 12 and 26

For the between-day and within-day glucose variability, the variables will take a log-transformation before performing the MMRM analysis.

The proportion of the patients with HbA1c $<7.0\%$ (or $\leq 6.5\%$) will be analyzed based on the multiple imputation with the following steps: 1) imputing the missing values in the continuous HbA1c by treatment, 2) dichotomizing the “complete” continuous HbA1c into binary based on the threshold, then 3) fitting the logistic regression model at each scheduled post-baseline visit, and 4) using Rubin’s rule to combine the results. In the logistic regression model, the independent variables of treatment, country, baseline HbA1c value will be used.

The above analyses may be repeated to compare LY3209590 (by pooling LY3209590 Algorithm 1 and LY3209590 Algorithm 2) with insulin degludec.

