5.10.4. Vital Signs and Body Weight

Vital signs and weight will be summarized by treatment group and visit. Change from baseline (last nonmissing value up to Visit 3) to postbaseline value for vital signs and weight will be summarized by treatment group and visit for patients who have both a baseline and at least 1 postbaseline result.

Treatment differences in mean change will be assessed using MMRM. The MMRM model will be used for the analysis during the treatment period and will contain the terms for treatment, baseline value, visit, and visit-by-treatment interaction as factors; patient as random effect; and CS as the variance-covariance structure. Only scheduled measures will be included in the MMRM analyses.

An analysis of covariance (ANCOVA) will also be conducted for the last nonmissing values during the study including the safety follow-up visit for the Safety Population. The ANCOVA model will use treatment, baseline value of the dependent variable as covariates.

The percentages of patients with treatment-emergent high or low vital signs at any time after randomization will be summarized and compared between treatment groups using Fisher's exact test. A treatment-emergent high result is defined as a change from a value less than or equal to the high limit (140 mm Hg for systolic blood pressure, 90 mm Hg for diastolic blood pressure, and 100 bpm for pulse) at baseline to a value greater than the high limit at any time that meets the specified change criteria after randomization. A treatment-emergent low result is defined as a change from a value greater than or equal to the low limit (90 mm Hg for systolic blood pressure, 50 mm Hg for diastolic blood pressure, and 50 bpm for pulse) at baseline to a value less than the low limit at any time that meets the specified change criteria after randomization. Patients with missing baseline measures will be excluded from this analysis unless otherwise specified. Scheduled visits, unscheduled visits, and retest measurements will be included in this analysis. [Table BDCP.3](#) will be used to define the low and high limits and change thresholds.

Table BDCP.3. Categorical Criteria for Abnormal Treatment-Emergent Blood Pressure and Pulse Measurement

Parameter	Low	High
Systolic BP (mm Hg) (Supine or sitting)	≤ 90 and decrease from baseline ≥ 20	≥ 140 and increase from baseline ≥ 20
Diastolic BP (mm Hg) (Supine or sitting)	≤ 50 and decrease from baseline ≥ 10	≥ 90 and increase from baseline ≥ 10

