5.10.5. Laboratory Measures

The data from laboratory testing will be summarized by treatment group and visit. Change from baseline (last nonmissing value up to Visit 3) to postbaseline value for laboratory tests (except for FSG, HbA1c, and Antibody) will be summarized for patients who have both a baseline and at least 1 postbaseline result. Treatment differences in mean change for these laboratory tests will be evaluated using MMRM model. The MMRM model will be used for the analysis during the treatment period and will contain the term for treatment, baseline value, visit, and visit-by-treatment interaction as factors, patient as random effect, and compound symmetric as the variance-covariance structure. Analyses will be provided in both international units (SI) and conventional units (CN). The MMRM analysis will only include lab tests for the scheduled visits specified in the protocol. For some selected laboratory measures, log-transformed value will be

used in MMRM when necessary, and the geometric LS means as well as the percentage change from baseline will be reported.

The last nonmissing values during the study including the safety follow-up visit for the Safety Population will also be analyzed by an ANCOVA model. The ANCOVA model will use treatment, baseline value of the dependent variable as covariates. For some selected laboratory measures, log-transformed value will be used in the ANCOVA model.

The percentages of patients with treatment-emergent abnormal laboratory results at any time after randomization (including the treatment period and follow-up period) will be summarized and compared between treatment groups using Fisher's exact test. A treatment-emergent abnormal result is defined as a change from normal at baseline to abnormal at any time after randomization. Covance reference ranges will generally be used to define the low and high limits. Patients with missing baseline lab measures will be excluded from this analysis unless otherwise specified. Scheduled visits, unscheduled visits, and retest measurements will be included in this analysis.

A lab listing in the Safety Population who had a treatment-emergent abnormal laboratory value during the study will be provided, including the actual measurement, abnormal result, and reference low or high limits.

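### Country, a randomization stratum, is missing from the CGM MMRM, and both strata are missing from the vital sign, weight, laboratory and ECG models: a possible small loss of precision for CGM, possible confounding by country for pooled safety

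*SAP*

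**What the plan says.** Protocol 6.3 says that "the randomization will be stratified by baseline HbA1c" in two classes, cut at 8.5%, and by country. The models use these strata unevenly.

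- **Primary (SAP 5.7):** "The MMRM model will include treatment (LY3209590 Algorithm 1, insulin degludec), country, visit, and treatment by visit interaction", plus baseline HbA1c.
- **Secondary efficacy (SAP 5.8):** analysed "using the same MMRM model as the primary analysis with the addition term of HbA1c strata" for the non-HbA1c measures, so with both strata.
- **CGM, continuous (SAP 5.11.2):** "The model will include the treatment, HbA1c stratum (<8.5% or >=8.5%), baseline value of the dependent variable, visit", and treatment by visit. The HbA1c stratum is in; country is not.
- **CGM, binary and episode counts (SAP 5.11.2):** "The binary variables will be analyzed using a longitudinal logistic regression", with no country among its listed terms. For the negative binomial model of episodes, "The model will include treatment, baseline HbA1c, baseline incidence for the dependent variable".
- **Vital signs and weight (SAP 5.10.4):** the MMRM "will contain the terms for treatment, baseline value, visit, and visit-by-treatment interaction as factors". Neither stratum is listed.
- **Laboratory (SAP 5.10.5):** the MMRM "will contain the term for treatment, baseline value, visit" and visit by treatment. Neither stratum is listed. The ECG model in SAP 5.10.6 has the same terms.
- **ANCOVA on last values (SAP 5.10.4 to 5.10.6):** treatment and baseline value only.

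SAP 5.1 and 5.10 compare pooled LY3209590 (Algorithm 1 plus Algorithm 2) with degludec for safety. SAP 5.1 and 5.11.1 compare Algorithm 1 with degludec for CGM. SAP 5.1 already defines pooled country, with Puerto Rico counted in the US. The SAP gives no reason for leaving the strata out.

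**The concern.** Balancing the arms on a factor and then leaving it out of a linear model keeps that factor's variance in the error term. The model-based standard error is then larger than the real sampling variation of the treatment difference. Some of the precision bought by stratifying is given away on CGM outcomes such as time in range.

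The choice also departs from the SAP's own practice. The 6-point profiles are read from the CGM device (Protocol 4.1.1 and 8.2.4), and their within-day and between-day variability is analysed with country (SAP 5.8). The same kind of variability measure from the downloaded CGM data is analysed without it. Fasting serum glucose is adjusted for country; the other laboratory tests are not.

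For pooled safety the issue is of another kind. Protocol Appendix 12 records, for amendment (c), that the randomization distribution could differ by country because Algorithm 2 was not offered in the EU. This is used here only as a fact about how some participants were allocated. If the pooled LY3209590:degludec ratio differs between countries, a model without country mixes country differences into the treatment difference.

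**Working it through.** **1. The plan's own figure.** The plan gives no number for the effect of country. Its sample size (Protocol 9.2: margin 0.4, SD 1.1, true difference 0, two-sided alpha 0.10, power 80%) reproduces:

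n per arm = 2 × (1.1/0.4)² × (1.645 + 0.842)² = 2 × 7.5625 × 6.18 ≈ 93.5, so 94, against 95 stated. Power at 95 per arm is 80.5%, and 190/0.8 = 237.5, so 238 randomized. That calculation concerns the primary endpoint, whose model includes country.

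**2. CGM linear MMRM, Algorithm 1 versus degludec, taken as 1:1 in every country.** Let R² be country's share of the *residual* variance after baseline value, HbA1c stratum and visit. The documents give no R², so a range is assumed.

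- Interval width ratio, country omitted to included: 1/√(1 − R²)
- True size of the nominal 0.10 test: 2 × [1 − Φ(1.645/√(1 − R²))]
- Equivalent loss of sample: 1/(1 − R²) − 1

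| Assumed R² | Width ratio | True size | Sample equivalent |
|---|---|---|---|
| 0% | 1.00 | 0.100 | 0% |
| 2% | 1.01 | 0.097 | 2% |
| 5% | 1.03 | 0.092 | 5% |
| 10% | 1.05 | 0.083 | 11% |

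A simulation of a country-stratified ANCOVA (190 participants, 5 equal countries assumed, 6,000 runs) gave width ratios of 1.00, 1.01, 1.03 and 1.05. Sizes with country omitted were 0.105, 0.097, 0.094 and 0.083. With country included, sizes were 0.101 to 0.105.

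**3. Pooled safety comparison.** Neither the number of Algorithm 2 participants nor the earlier ratio is given, so this is only an illustration. Assumptions: 118 per group, half in the US (59), then k extra LY3209590 participants, all in the US; a linear model; a US versus non-US difference of d standard deviations; no treatment effect.

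Without country, the bias is d × (US share in LY3209590 − US share in degludec). For k = 28 the shares are (59 + 28)/(118 + 28) = 0.596 and 0.500. With d = 0.5 the bias is 0.5 × 0.096 = 0.048 SD; the simulation gave 0.046.

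| Extra k | Bias (SD), d = 0.2 / 0.5 / 0.8 | Size at nominal 0.10, d = 0.2 / 0.5 / 0.8 |
|---|---|---|
| 10 | 0.01 / 0.02 / 0.03 | 0.098 / 0.092 / 0.083 |
| 28 | 0.02 / 0.05 / 0.08 | 0.100 / 0.111 / 0.140 |
| 50 | 0.03 / 0.08 / 0.12 | 0.110 / 0.152 / 0.236 |

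With country in the model, bias was about 0 and size about 0.10 throughout. Two forces compete: unused balance lowers the size, and unequal allocation raises it. Which one wins depends on figures the documents do not give.

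**4. CGM logistic model.** Simulation with 190 participants, two countries, a true log odds ratio of 0.8, and country log odds ratios of 0.5 / 1.0 / 1.5 (all assumed):

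- Country omitted: estimates 0.81 / 0.77 / 0.70, standard errors 0.298 / 0.297 / 0.296.
- Country included: estimates 0.82 / 0.82 / 0.81, standard errors 0.301 / 0.309 / 0.322.

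Here omission pulls the estimate towards zero and the standard error is slightly smaller, so the linear-model result does not carry over.

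**The case against.** A reader might infer that every model without country has wider intervals and conservative tests. The documents do not support that. The result needs a linear model and the same allocation ratio in each country. The safety models pool Algorithm 2, so the ratio may not be constant, and working step 3 shows the size can fall on either side of 10%. The compound-symmetry covariance fixed for the vital sign, laboratory and ECG models can also misstate standard errors in either direction. For the CGM logistic model no claim of wider intervals can be made.

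Even for the CGM MMRM, the loss occurs only if country predicts the outcome beyond the existing terms. A stable country difference would be partly absorbed by the baseline value, so R² may be near zero. This stands, and it is why the range starts at 0%.

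Confounding in the safety models is likewise a possibility, not a finding. The protocol's amendment rationale speaks only of a limited number of Algorithm 2 participants. An earlier scheme that kept the pooled ratio equal across countries would remove the problem.

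The stakes are modest. The primary and secondary efficacy MMRMs carry country. CGM time in range is exploratory, and SAP 5.11.1 makes no multiplicity adjustment. Protocol 9.4.6.4 describes laboratory data descriptively, and 9.4.6.5 treats ECG mainly as safety monitoring. The protocol fixes no terms for these models, so the SAP contradicts nothing. No document shows that HbA1c stratum predicts ECG or vital signs; the reason to include it is that it was a stratification factor. All of this limits the weight of the point, but none of it is a reason to omit the strata.

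**Conclusion.** The point holds as a minor one. The SAP leaves country out of the CGM MMRM, and both strata out of the vital sign, weight, laboratory and ECG models, without explanation and against its practice for efficacy.

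- **CGM linear MMRM:** intervals 0 to 5% too wide and a true size of 10.0 to 8.3% for the nominal 10% test. This rests on an assumed residual R² of 0 to 10% and a 1:1 ratio within country.
- **Pooled vital sign, weight, laboratory and ECG comparisons:** possible confounding by country, with test size on either side of 10%. The direction and amount cannot be stated, because the number of Algorithm 2 participants and their allocation by country are not given. It would be wrong to reassure readers that these tests are conservative.
- **Primary non-inferiority test:** unaffected; its model includes country.

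**What to change.** Before database lock, amend the SAP as follows.

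1. Add pooled country, as defined in SAP 5.1, to the CGM MMRM in 5.11.2.
2. Add pooled country and HbA1c stratum (<8.5%, ≥8.5%) to the MMRM and ANCOVA models for vital signs, weight, laboratory measures and ECG in 5.10.4 to 5.10.6.
3. If a term is deliberately left out, give the reason.
4. Report the pooled LY3209590 and degludec counts by country, so that readers can see whether allocation differed.

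This is a free improvement: one or two fixed effects in models already planned, using factors known for every participant at randomization. It should be prespecified, because SAP section 6 says the study team is unblinded to treatment, and covariates added after results are seen would be less credible. The diary hypoglycemia rate and incidence models in SAP Table BDCP.1 also list no country term. They were not sized here but should be considered in the same revision.

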5.11.2.1. Hypoglycemia

- Percentage and Duration (in minutes) of time per day where glucose values are within a hypoglycemic range (defined as <70 mg/dL [3.9 mmol/L]) during the nighttime period (defined as midnight to 0600 hours), the daytime period (defined as 0600 hours to 2400 hours) and a 24-hour period.
- Percentage and Duration (in minutes) of time per day where glucose values are within a hypoglycemic range (defined as <54 mg/dL [3.0 mmol/L]) during the nighttime period, the daytime and a 24-hour period.
- Percentage and Duration (in minutes) of time per day where glucose values are within a hypoglycemic range (defined as <70 mg/dL [3.9 mmol/L] and ≥ 54 mg/dL [3.0 mmol/L]) during the nighttime period, the daytime period and a 24-hour period.
- Incidence of hypoglycemic episodes (defined as <70 mg/dL [3.9 mmol/L], or <54 mg/dL [3.0 mmol/L] or <70 mg/dL [3.9 mmol/L] and ≥ 54 mg/dL [3.0 mmol/L]) during the nighttime period, the daytime period and a 24-hour period.
- Rate of hypoglycemic episodes (defined as <70 mg/dL [3.9 mmol/L], or <54 mg/dL [3.0 mmol/L] or <70 mg/dL [3.9 mmol/L] and ≥ 54 mg/dL [3.0 mmol/L]) during the nighttime period, the daytime period and a 24-hour period.
- Duration (in minutes) of each individual hypoglycemic episode (defined as <70 mg/dL [3.9 mmol/L], or <54 mg/dL [3.0 mmol/L] or <70 mg/dL [3.9 mmol/L] and ≥ 54 mg/dL [3.0 mmol/L] for at least 15 minutes).

5.11.2.2. Hyperglycemia

- Percentage and Duration (in minutes) of time per day glucose values are within a hyperglycemic range (defined as >180 mg/dL [10.0 mmol/L] and ≤ 250 mg/dL [13.9 mmol/L]) during the nighttime period, the daytime period and a 24-hour period.
- Percentage and Duration (in minutes) of time per day glucose values are within a hyperglycemic range (defined as >250 mg/dL [13.9 mmol/L]) during the nighttime period, the daytime period and a 24-hour period.

5.11.2.3. Normal Range

Percentage and Duration (in minutes) of time per day glucose values are within a normal glycemia range (defined as between 70 mg/dL and 180 mg/dL [3.9 and 10.0 mmol/L]) inclusive during the nighttime period, the daytime period and a 24-hour period.

5.11.2.4. Glycemic Variability

- Low Blood Glucose Index (LBGI) during the nighttime period and a 24-hour period.
- High Blood Glucose Index (HBGI) during the nighttime period and a 24-hour period.
- Combined blood glucose risk index (BGRI derived as LBGI + HBGI) during the nighttime period and a 24-hour period.
- Within-day and between-day glucose CV during the nighttime period and a 24-hour period.
- Within-day and between-day glucose CV $\leq 36\%$ during the nighttime period and a 24-hour period.
- Within-day and between-day glucose SD during the nighttime period and a 24-hour period.
- Mean of daily differences (MODD) during the nighttime period and a 24-hour period

5.11.2.5. Ambulatory Glucose Profile

The ambulatory glucose profile (AGP) during the 24-hour period will be generated with interquartile ranges, at treatment-group level by visit (baseline, Week 6, Week 12, and Week 26), based upon the observed CGM measures.

